5 PARTICIPANT SELECTION AND ENROLMENT

5.1 IDENTIFYING PARTICIPANTS

Potential study participants will be approached through the NHS Research Scotland (NRS) Primary Care Network which is directed by co-investigator, [name]. NRS Primary Care Network will arrange for letters to be sent to each potential participant from their registered General Practitioner as we have previously undertaken for other research projects. For example, an early lung cancer detection study recruited 12,000 patients (from 150-200 General Practices) having sent out 77,066 invitation letters. The letters will be printed and posted by Docmail, a ISO/IEC 27001 accredited company. We will also have the option of approaching the Scottish Health Research Register or SHARE (<https://www.registerforshare.org>). This is a national register of Scottish residents who are willing and keen to take part in research with over 200,000 people currently registered. This has been an extremely useful resource for other trials and enables pre-identification of eligible patients. Finally, we will set up a website where individuals can volunteer to participate in the trial (self-referral).

A Study Within a Trial (SWAT) will be embedded into the main study. This SWAT will assess the impact of two interventions on response rates to the invitation letters sent out by the Primary Care Network. One of the interventions is the inclusion of a one-page Participant Information Sheet with the invitation letter. If a participant proceeds to attend for a screening visit, they will be provided with the standard length version before their appointment. The protocol for this study is detailed in Appendix 1.

5.2 CONSENTING PARTICIPANTS

Potential participants will be provided with an information sheet prior to attendance at the study clinic. They will attend the Edinburgh Clinical Research Facility where eligibility will be confirmed, and consent obtained by appropriately trained and delegated research staff and recorded in the participant's medical records.

5.3 INELIGIBLE AND NON-RECRUITED PARTICIPANTS

All ineligible and non-recruited participants attending the CRF will be recorded on the screening log with a reason given (if known).

5.4 RANDOMISATION

5.4.1 Randomisation Procedures

Participants will be randomised using a web-based randomisation service (managed by the Edinburgh Clinical Trials Unit). Participants will be allocated to receive either CTCA plus standard care or standard care only in a 1:1 ratio and will be minimised by ASSIGN score (<10, 10-20 and >20) and will include a random element.

5.4.2 Intervention Allocation

Participants allocated to CTCA will have an appointment arranged to complete the scan.

5.5 WITHDRAWAL OF STUDY PARTICIPANTS

Participants are free to withdraw from the study at any point or a participant can be withdrawn by the Investigator. After withdrawal, no further data will be collected about the participant (including long term data linkage). If withdrawal occurs, the primary reason for withdrawal will be documented in the participant's case report form, if possible. Data collected up until that point will be retained. To safeguard rights, the minimum personally identifiable information possible will be collected. If a participant chooses to withdraw from the study, they are informed to contact the trial team if they want any blood samples stored for future research to be destroyed. Not wishing to attend the CTCA scan or complete trial questionnaires does not constitute withdrawal from the study. These requests will be documented in the eCRF and the participant will continue to have an 'Active' status and be followed up.

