6.4 LONG TERM FOLLOW UP ASSESSMENTS

Outcome measures will be obtained through the electronic Data Research and Innovation Service (eDRIS) and the General Register Office as we have successfully achieved with the SCOT-HEART [SCOT-HEART, 2015; Williams et al, 2016; SCOT-HEART, 2018] and HighSTEACS [Shah et al, 2015a; Shah et al, 2015b] trials. We will capture all hospital admission events and will have access to clinical records and imaging as required through NHS Safe Havens. We will collect clinical outcomes, coronary procedures and prescribing data through NHS data systems and eDRIS as we have for the [SCOT-HEART, 2015; Williams et al, 2016; SCOT-HEART, 2018] trial. These datasets alongside unscheduled care (ambulance service, NHS 24 etc) and social care will be used to evaluate healthcare resource use for the health economic analysis.

Health economic (healthcare-related quality of life (EQ-5D-5L) and NHS resource use) and lifestyle questionnaires will be sent to all study participants at 6 months. The first 3,000 participants who respond to these questionnaires will be followed up again at 2 years.

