8 STATISTICS, HEALTH ECONOMICS AND DATA ANALYSIS

8.1 SAMPLE SIZE CALCULATION

There is uncertainty in this asymptomatic primary care population as to the underlying 5-year event rate for the primary outcome of coronary heart disease death or non-fatal MI. We believe the closest match to our proposed study population will be that observed in the non-anginal chest pain group in the SCOTHEART trial (18/735, or around 2.5% at 5 years)

[SCOT-HEART 2018]. Again, from the SCOTHEART trial, there were treatment effects equating to a hazard ratio of between 0.45 and 0.65 across many subgroups with differing levels of risk. Outcome data (e.g. at 5 years) will not mature until after recruitment is finished. If we randomise 6,000 participants 1:1 to CTCA or ASSIGN risk score then if the control (treatment based on ASSIGN score) 5-year primary outcome rate is 2.0, 2.5, 3.0, 3.5 or 4.0 we will have 90% power at a 5% level of significance to detect treatment effects corresponding to hazard ratios of 0.49, 0.54, 0.57, 0.60 and 0.62 (corresponding to observing an aggregate of around 90, 116, 142, 169 and 196 events). Where insufficient events have accrued, we do have the option of further extending follow up at minimal cost. The Trial Steering Committee (TSC) will review the event rate at 4 years after study start and recommend whether to extend recruitment including a sample size re-estimation. The TSC will also consider factors such as event rates in sub-groups of age (40-50 vs 50-70 year olds) and pre-existing statin use.

The Data Monitoring Committee will review the results of formal interim analyses under a Lan DeMets alpha spending approach (using O'Brien Fleming boundaries) at 4, 5, 6 and 7 years after study start. This will allow the findings of the study to be declared when they have become definitive – either for overwhelmingly evidence of benefit or for futility. Full details of the group sequential design and the operationalisation of interim analyses will be given in the comprehensive Statistical Analysis Plan.

We therefore propose to recruit at least 6,000 subjects over the initial 4-year recruitment period.

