8.2 PROPOSED STATISTICAL ANALYSES

All statistical analyses will be governed by a comprehensive Statistical Analysis Plan, authored by the study statistician and approved by both the Trial Steering Committee and independent Data Monitoring Committee. The primary outcome of time-to-first coronary heart disease death or non-fatal MI will be compared (using an intention-to-treat approach) between the randomised groups (risk score or CTCA guided management) using a Cox proportional hazards regression model. This will adjust for pre-specified prognostic covariates, such as age, sex, baseline 10-year cardiovascular risk score, risk factors such as diabetes, and prior statin therapy. In the case of non-proportional hazards, we will use a restricted mean survival time (RMST) approach. Secondary outcomes (e.g. lifestyle changes such as smoking, body weight, physical activity, diet; cardiovascular medications (use and compliance with); quality of life; procedural outcomes (e.g. invasive coronary angiography and coronary revascularisation); major adverse cardiovascular events; mortality) will be analysed using a model suitable to the nature of the outcome – e.g. time to event as per the primary outcome; or binary or ordinal logistic regression; or linear regression; or negative binomial regression. The study is not powered for subgroup analyses so these will be undertaken as exploratory analyses to assess moderation of treatment effects. For the mechanistic outcomes, we may use mediation type analyses (e.g. causal models using instrumental variables). We would also intend to build both prediction models (to predict response to intervention) and prognostic models (to predict disease course, adjusting for any intervention effect). For the primary outcome (obtained through record linkage into routine data), the level of missingness is expected to be negligible. For some secondary outcomes (e.g. the patient reported outcomes), the level of missingness may be around 20%, and so sensitivity type analyses (e.g. assuming data are

CR007-T02 v2.0

missing at random; or possibly not missing at random i.e. informatively missing) will be considered to explore whether the findings are robust to the patterns of missingness.

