11.2.1 Informed Consent

The Investigator is responsible for ensuring informed consent is obtained before any protocol specific procedures are carried out. The decision of a participant to participate in clinical research is voluntary and should be based on a clear understanding of what is involved.

Participants must receive adequate oral and written information – appropriate Participant Information and Informed Consent Forms will be provided. The oral explanation to the participant will be performed by the Investigator or qualified delegated person, and must cover all the elements specified in the Participant Information Sheet and Consent Form.

The participant must be given every opportunity to clarify any points they do not understand and, if necessary, ask for more information. The participant must be given sufficient time to consider the information provided. It should be emphasised that the participant may withdraw their consent to participate at any time without loss of benefits to which they otherwise would be entitled.

The participant will be informed and agree to their medical records being inspected by representatives of the sponsor(s).

The Investigator or delegated member of the trial team and the participant will sign and date the Informed Consent Form(s) to confirm that consent has been obtained. The participant will receive a copy of this document and a copy filed in the Investigator Site File (ISF) and participant's medical notes (if applicable).

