11.7 END OF STUDY

The end of study is defined as the last participant's last 6-month follow up. However, electronic health record follow up is planned thereafter.

The Investigators or the co-sponsor(s) have the right at any time to terminate the study for clinical or administrative reasons.

The end of the study will be reported to the REC, and R+D Office(s) and co-sponsors within 90 days, or 15 days if the study is terminated prematurely. The Investigators will inform participants of the premature study closure and ensure that the appropriate follow up is arranged for all participants involved. End of study notification will be reported to the co-sponsors via email to [contact]

A summary report of the study will be provided to the REC within 1 year of the end of the study.

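### Section 5.5 stops record linkage, the source of the primary outcome, after every withdrawal, including one decided by the investigator when the participant has not refused linkage

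*Protocol*

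**What the plan says.** Protocol section 5.5 gives two routes out of the trial. Participants may leave at any time, or "a participant can be withdrawn by the Investigator". The rule that follows makes no distinction between them: "After withdrawal, no further data will be collected about the participant (including long term data linkage". The section sets no criteria for an investigator's decision and no step at which a departing participant is asked about linkage. Data gathered before withdrawal are kept.

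Section 5.5 also narrows what counts as withdrawal: "Not wishing to attend the CTCA scan or complete trial questionnaires does not constitute withdrawal from the study". Such participants keep active status and remain in follow-up.

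Linkage carries the primary endpoint. Section 6.4 states: "Outcome measures will be obtained through the electronic Data Research and Innovation Service (eDRIS) and the General Register Office". Section 8.2 plans an intention-to-treat Cox analysis and adds: "For the primary outcome (obtained through record linkage into routine data), the level of missingness is expected to be negligible". Section 11.7 places the end of study at the last participant's 6-month follow-up, after which "electronic health record follow up is planned thereafter". Section 11.2.1 sets out the participant's right: "the participant may withdraw their consent to participate at any time".

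**The concern.** Stopping linkage is right when a participant withdraws consent to it. That reason does not cover an investigator's decision, which the participant may not have sought and which says nothing about their view of passive follow-up. It covers only in part a participant who wants no more contact but was never asked about linkage.

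In both cases section 5.5, followed as written, ends primary-outcome follow-up that would cost the participant nothing. Because this is a data-collection rule, no analysis plan can recover what was not collected. Section 8.1 notes that "Where insufficient events have accrued, we do have the option of further extending follow up at minimal cost". A longer follow-up can replace lost events, but it does not return the withdrawn participants' later outcomes to the intention-to-treat comparison.

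At stake are a small loss of events and, only if loss were related to both arm and risk, some bias. Section 5.5 does not contradict the intention-to-treat analysis or the expectation of negligible missingness. It makes an avoidable exception to them.

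**Working it through.** **Inputs from Protocol section 8.1.** 6,000 randomised 1:1; 5% significance level (two-sided assumed); 90% power; control 5-year rates 2.0, 2.5, 3.0, 3.5 and 4.0%; hazard ratios 0.49, 0.54, 0.57, 0.60 and 0.62; about 90, 116, 142, 169 and 196 events. **Assumed, because no rate is given:** 1% to 5% withdrawn. Only part of any such loss is avoidable, so the losses below are upper bounds.

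**Step 1: reproduce the protocol's events.** The CTCA-arm rate is p2 = 1 − (1 − p1)^HR, and events = 3000 × (p1 + p2). For the 2.5% row, p2 = 1 − 0.975^0.54 = 0.01358, so events = 75 + 40.7 = 115.7. Power uses a two-proportion comparison, Φ(√n·(p1 − p2)/√(p1(1 − p1) + p2(1 − p2)) − 1.96), with n per arm. The last two columns show 5% lost from each arm at randomisation, so n = 2850.

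| Control rate | HR | Events, protocol | Events, recomputed | Power, n = 3000 | Events lost at 5% | Power, n = 2850 |
|---|---|---|---|---|---|---|
| 2.0% | 0.49 | 90 | 89.6 | 90.1% | 4.5 | 88.5% |
| 2.5% | 0.54 | 116 | 115.7 | 89.6% | 5.8 | 88.0% |
| 3.0% | 0.57 | 142 | 141.6 | 90.4% | 7.1 | 88.9% |
| 3.5% | 0.60 | 169 | 168.4 | 90.2% | 8.4 | 88.6% |
| 4.0% | 0.62 | 196 | 195.0 | 90.7% | 9.7 | 89.2% |

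All five event totals reproduce. They correspond to 5 full years of follow-up in all 6,000 with no loss. Losing 5% costs about 1.5 power points in every row.

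**Step 2: base case (2.5%, HR 0.54), equal loss in both arms.** One event is lost per 6000/115.7 = 52 people withdrawn at randomisation, or per about 104 if withdrawals are spread evenly over 5 years. Power for the even spread is approximated by halving the loss.

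| Withdrawn | Timing | Events lost | n per arm used | Power |
|---|---|---|---|---|
| 1% (60 people) | at randomisation | 1.2 | 2970 | 89.3% |
| 1% | evenly over 5 years | 0.6 | 2985 | 89.5% |
| 5% (300 people) | at randomisation | 5.8 | 2850 | 88.0% |
| 5% | evenly over 5 years | 2.9 | 2925 | 88.8% |

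**Step 3: extra follow-up that would replace the events.** With exponential times, λ1 = −ln(0.975)/5 and λ2 = 0.54·λ1. Solving n·(2 − e^(−λ1·T) − e^(−λ2·T)) = 115.7 for T gives 0.6 months beyond 5 years at n = 2970, and 3.2 months at n = 2850.

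**Step 4: bias, as illustration only.** Suppose the true HR is 1.00 with a 2.5% rate in both arms. Suppose also that 5% of the CTCA arm alone is lost at randomisation, at twice the risk of those who stay, with no covariate adjustment. The apparent HR is 1/(1 − 0.05 + 0.05 × 2) = 0.952. Events seen are 75 in the control arm and 2850 × 0.025/1.05 = 67.9 in the CTCA arm. The standard error of the log HR is √(1/75 + 1/67.9) = 0.168, and the two-sided type I error is 6.0%. With withdrawal spread evenly over 5 years, simulation (6,000 runs) gives an HR of 0.97 and a type I error of about 5%.

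**The case against.** The strongest reply is that section 5.5 already does most of what is asked. After the baseline visit, the participant is asked for little more than the scan and the questionnaires, and declining either leaves them in follow-up. A participant who still withdraws is mostly leaving passive follow-up, so withdrawal comes close to refusing linkage. The investigator route may hardly be used: the intervention is one diagnostic scan, the protocol describes no case for withdrawing someone, and the most obvious one, invalid consent, should end linkage anyway. The consent form is not shown and may promise that linkage stops. Section 8.1 allows for at least 6,000 participants, longer follow-up and a sample size re-estimation. The bias example needs one-sided, early, high-risk loss, and the planned Cox model adjusts for several prognostic covariates.

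Most of this stands as a limit on size. The affected group is narrow and could be close to empty, nothing shows differential loss, and the assumed rates include genuine refusals that no amendment should recover. What does not stand is equating withdrawal with refusal of linkage. The text does not say so, and it cannot be true of a decision taken by the investigator. The unseen consent wording affects how the change is made, in particular for those already enrolled. It does not supply a reason for ending linkage when nobody has refused it.

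**Conclusion.** The concern holds, as a cheap improvement and not as a threat to the result. The avoidable loss is confined to investigator withdrawals and to participants recorded as withdrawn without being asked about linkage. For an assumed 1% to 5% withdrawn in total, the base-case cost is at most 1.2 to 5.8 events and 0.3 to 1.6 power points, and the avoidable part is smaller. Bias would need loss related to both arm and risk, which the documents do not show. Even the deliberately one-sided illustration takes type I error only to about 6%. These sizes rest on assumed withdrawal rates, on constant hazards for the timing calculations, and on a two-sided 5% test. The reading of section 5.5 rests on its text alone.

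**What to change.** Amend section 5.5 in two places:

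- Withdrawal by the investigator stops study procedures and contact but not record linkage, unless consent is found to be invalid or the participant refuses linkage.
- A participant who asks to withdraw is asked whether linkage may continue. The answer is recorded in the eCRF, and linkage ends if they refuse. If no answer can be obtained, the consent wording decides.

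Apply the change prospectively, or with re-consent for those enrolled under the present text.

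The cost is a short amendment through the approvals in section 11.3, one eCRF field, and possibly a revised information sheet and consent form. Re-consent, if used, adds some work. No extra participants or visits are needed, and the right to refuse linkage is kept.

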6 STUDY ASSESSMENTS

6.1 STUDY ASSESSMENTS

At the study visit, participants will:

- Complete a clinical proforma with the study team member

- Have up to 45 mL of blood taken. A 5 mL serum gel tube will be used to assess lipid profile and renal function with excess blood being retained for future study biomarker analysis.
- Have blood pressure and heart rate taken
- Complete questionnaires on lifestyle and quality of life
- Have an ASSIGN score calculated

6.2 COMPUTED TOMOGRAPHY

Computed tomography will be performed with a 64-detector row (or more) scanner. Rate limiting medication (e.g beta blocker) will be prescribed as required to obtain a heart rate of <60 bpm at time of imaging. Glyceryl trinitrate (GTN) will be administered unless contraindicated. Non-contrast electrocardiogram-gated computed tomography will be performed for calcium scoring. Contrast enhanced electrocardiogram gated CTCA will be performed using iodinated contrast.

6.3 FEEDBACK OF RESULTS

The research team will provide all participants and their GPs written recommendations based on the current standard of care guidelines dependant on the results of their ASSIGN score or CTCA scan. Recommendations will include lifestyle advice, use of statins/antiplatelet therapy/ ACE inhibitors or referral to Cardiology. Feedback will also be given to participants and their GP about incidental findings from CTCA and referral for further treatment will be arranged by the research team. An NHS email account will be created to provide a point of contact for clinical queries following communication of the risk score and CTCA results.

6.4 LONG TERM FOLLOW UP ASSESSMENTS

Outcome measures will be obtained through the electronic Data Research and Innovation Service (eDRIS) and the General Register Office as we have successfully achieved with the SCOT-HEART [SCOT-HEART, 2015; Williams et al, 2016; SCOT-HEART, 2018] and HighSTEACS [Shah et al, 2015a; Shah et al, 2015b] trials. We will capture all hospital admission events and will have access to clinical records and imaging as required through NHS Safe Havens. We will collect clinical outcomes, coronary procedures and prescribing data through NHS data systems and eDRIS as we have for the [SCOT-HEART, 2015; Williams et al, 2016; SCOT-HEART, 2018] trial. These datasets alongside unscheduled care (ambulance service, NHS 24 etc) and social care will be used to evaluate healthcare resource use for the health economic analysis.

Health economic (healthcare-related quality of life (EQ-5D-5L) and NHS resource use) and lifestyle questionnaires will be sent to all study participants at 6 months. The first 3,000 participants who respond to these questionnaires will be followed up again at 2 years.

6.5 STORAGE AND ANALYSIS OF SAMPLES

Blood samples will be obtained by standard venesection and sent to Clinical Biochemistry Laboratories of the Royal Infirmary of Edinburgh for lipid analysis and renal function (5 mL serum gel tube). Up to an additional 40 mL of blood will be obtained and processed for future genetic and plasma biomarker discovery studies.

7 DATA COLLECTION

Study data will be entered into an electronic case report form (eCRF) developed by Edinburgh Clinical Trials Unit (ECTU). A source data plan will be created to indicate where the study data are originally documented. The study data obtained from electronic health records will be entered directly into the eCRF.

7.1 DATA MANAGEMENT

7.1.1 Personal Data

Personal data will be stored securely within ECTU according to their standard operating procedures. This will include the patient's name, address and CHI number.

7.1.2 Transfer of Data

Identifiable data collected or generated by the study (including personal data) will not be transferred to any external individuals or organisations outside of the Sponsoring organisation(s). We do intend to share anonymised data with external collaborators and scientists.

